4.6 Steps to be Taken to Control or Mitigate Risks

Users will be assessed by a Research Team member to establish that no infection is present in the wound site on enrolment and assessment.

Subjects will be asked to measure and record their temperature daily and to contact nurse support if there is an elevation in temperature.

If subjects record a pyrexia greater than 38 degrees. The Subject will contact the Research team where it will be recorded. Subject will be asked to recheck temperature following 1 hour without temperature reducing medication (paracetamol ibuprofen et). If pyrexia persists, subject will be directed to attend GP for immediate follow up and the use of the study device will be stopped.

Research nurse to assess whether pyrexia is device related.

If it is not device related, a telephone contact log is to be filled in and reported to the sponsor.

[figure not shown]
If it is device related, an adverse is to be recorded and reported to sponsor

CE-GAX001-01

V4.0

CR: 144

Process Flow for Pyrexia >38 Degrees

The dressing used in this study is provided sterile.

The fastener used in this study is used externally and does not touch the skin during use. Material base and Velcro is medical grade.

The dressing and fastener will be CE marked by the legal manufacturer (Planet Medical Products Co. Ltd., China). The manufacturer is ISO13485 certified.

Hidramed AX fabric is an OEKO-TEX® certified material. The Hidramed AX full produced garment has been evaluated in accordance with ISO 10993 and it is biocompatible for its intended use. Verification and validation testing will be performed to evaluate the design of the garment. Hidramed Solutions will CE mark the device in accordance with the medical device directive 93/42/EEC.

CE-GAX001-01

V4.0

CR: 144

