15 ADVERSE EVENTS, ADVERSE DEVICE EVENTS AND DEVICE DEFICIENCIES

15.1 Definition: Adverse Event (AE)

An Adverse Event (AE) is defined as any untoward medical occurrence, unintended disease or injury, or any untoward clinical signs (including abnormal laboratory findings) in subjects, users or other persons, whether or not related to the investigational medical device.

This includes:

- Events related to the investigational medical device
- Events related to procedures involved (any procedure in the clinical investigation plan)
- For users and other persons, this definition is restricted to events related to the investigational medical device.

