15.2 Definition: Adverse Device Effect (ADE)

An Adverse Device Effect (ADE) is defined as an adverse event related to the use of an investigational medical device resulting from insufficient or inadequate instructions for use, deployment, implantation, installation, operation, any malfunction, user error, or intentional misuse of the investigational medical device

Subjects will be fully trained on how to use the device and be provided with instructions for use. Subjects can contact research nurse at any time if unsure, and can send daily comments to the researcher through daily check ins.

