15.3 Definition: Device Deficiency

An Adverse Device Effect (ADE) is defined as an adverse event related to the use of an investigational medical device resulting from insufficient or inadequate instructions for use, deployment, implantation, installation, operation, any malfunction, user error, or intentional misuse of the investigational medical device

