15.4 Serious Adverse Event

A Serious Adverse Event (SAE) is any event (whether or not associated with the investigational device) that:

- Results in death
- Leads to serious deterioration in the health of the subject, that either resulted in
- Life threatening illness or injury, or
- Permanent impairment of a body structure or a body function, or
- In-subject or prolonged hospitalization, or
- Medical or surgical intervention to prevent life threatening illness or injury or permanent impairment to a body structure or body function.
- Leads to foetal distress, foetal death or a congenital abnormality or birth defect

CE-GAX001-01

V4.0

CR: 144

This includes device deficiencies that might have led to a serious adverse event if a) suitable action had not been taken or b) intervention had not been made or, c) if the circumstances had been less fortunate. These are handled under the SAE reporting system.

Planned hospitalisation for a pre-existing condition, without serious deterioration in health, is not considered a serious adverse event.

Subjects who experience and adverse will be released to their primary care provider/GP and excluded from the study.

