15.6 Reporting Adverse Events

Any and all adverse events shall be captured by our independent trial implementation partner, The Clinical Research Platform Ireland.

Adverse events will be reported in accordance with MEDDEV 2.12-1 GUIDELINES ON A MEDICAL DEVICES VIGILANCE SYSTEM and QP025 Clinical Evaluation procedure.

When an event/incident occurs, a report is necessary; the event is recorded within the records outlined in QP025 Clinical Evaluation procedure, Appendix 1: Clinical Operations Document Listing by either the SMO, Research Coordinator or Investigator and returned to HidraMed Solutions within the timelines outlined in QP025 Clinical Evaluation procedure.

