15.7 Reporting Device Deficiencies

Any device deficiencies observed during the investigations shall be documented and controlled and processed by Hidramed Solutions.

A root cause analysis shall be undertaken by Hidramed Solutions Design & Development and Quality Assurance teams, with appropriate steps taken to remove risk of future reoccurrence.

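### Section 4.6 ties the adverse-event record for a fever to device-relatedness, contrary to 15.1 and 15.6, and 15.3 gives no definition that covers a harmless device failure

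*Combined protocol and SAP*

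**What the plan says.** **Fever.** Under section 4.6 a subject with a temperature above 38 degrees contacts the research team, who record it. The subject rechecks after 1 hour without fever-reducing medication. If the fever persists, the subject is sent to the GP and the device is stopped. The research nurse then judges relatedness, and the pathway splits:

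- Not related: "If it is not device related, a telephone contact log is to be filled in and reported to the sponsor".
- Related: "If it is device related, an adverse is to be recorded and reported to sponsor". A word, presumably *event*, is missing.

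Section 15.1 defines an adverse event as one that counts "whether or not related to the investigational medical device". Section 15.6 adds: "Any and all adverse events shall be captured by our independent trial implementation partner". The schedules in 6.4.1 and Appendix 1 have an adverse-events row and a temperature row, both marked at every time point.

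**Device failure.** Section 15.2 states: "An Adverse Device Effect (ADE) is defined as an adverse event related to the use of an investigational medical device". Section 15.3 has the device-deficiency heading, but from the abbreviation on its text reads "ADE) is defined as an adverse event related to the use of an investigational medical device" and continues as in 15.2. Section 15.7 requires: "Any device deficiencies observed during the investigations shall be documented and controlled and processed by Hidramed Solutions". Section 15.4 sends to serious-adverse-event reporting those deficiencies that might have led to a serious event.

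**Exclusion.** The last sentence of 15.4 reads: "Subjects who experience and adverse will be released to their primary care provider/GP and excluded from the study".

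**The concern.** Section 7.1 lists adverse events among the things the pilot is to evaluate, and section 4.1.1 uses temperature to watch for infection. The study is single-arm and unblinded (6.1.1), so there is no control group in which uneven recording would show up. If staff follow 4.6 as the specific instruction for fever, one relatedness judgement decides whether a fever becomes an adverse event. That judgement should be data on the record, open to later review, and not a condition for having a record.

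For device failures, retaining the dressing is the intended purpose (2.3), and secure retention is a claim (5.3). A dressing that comes loose without hurting anyone is the kind of event a deficiency record should be able to hold. The section meant to define that record defines something else.

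**Working it through.** The plan gives no figure on this point to reproduce. The check compares the sections with each other and adds a short illustration of scale.

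**Step 1: fever.** A fever that persists for an hour, sends the subject to the GP and stops the device is an untoward clinical sign. Relatedness is no part of the 15.1 definition, so both branches of 4.6 are adverse events under 15.1, and 15.6 requires both to be captured. Section 4.6 names an adverse-event record for one branch only. The two sections point to different records for the same fever.

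An unrelated fever would still appear in:
- the research team's record when the subject first makes contact (4.6), before relatedness is judged;
- the daily temperature data, which is the first check-in question (6.1.4, Appendix 7);
- the telephone contact log, which goes to the sponsor (4.6).

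So the fever remains in the study data. What can fail is its classification as an adverse event.

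**Step 2: the recheck.** Section 15.1 does not require a sign to persist. A correction to 4.6 should therefore not make the 1-hour recheck a new condition for recording.

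**Step 3: device failure.** There are three cases:
- Failure with harm: an adverse device effect under 15.2, and again under 15.3.
- Failure without harm that might have led to a serious event: covered by 15.4.
- Failure without harm and without that potential: meets no definition, because 15.2 and 15.3 both require an adverse event.

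Section 15.7 still asks for any deficiency to be documented. The duty exists, but the term for the third case is undefined.

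**Step 4: exclusion.** The 15.4 sentence can be read as any adverse event or as serious adverse events only. Under the first reading, every fever recorded as an adverse event would exclude a subject. The sentence sits under the serious-adverse-event heading. Section 4.3 handles adverse effects by stopping the device and contacting the nurse, and 6.3.4 suspends the garment for pyrexia. All of this suggests serious events only, but the text does not settle it.

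**Step 5: illustration of scale.** The sample size is n = 23 (7.2). Let p be a subject's 3-week chance of a confirmed fever judged unrelated. The plan gives no value, so p is assumed. The chance that at least one subject meets the 4.6 split is 1 − (1 − p)^23:

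| assumed p | result |
|---|---|
| 1% | 1 − 0.99^23 = 20.6% |
| 2% | 1 − 0.98^23 = 37.2% |
| 5% | 1 − 0.95^23 = 69.3% |
| 10% | 1 − 0.90^23 = 91.1% |

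Suppose 1 to 3 such fevers (also assumed) stayed in the log, with no other fever on the adverse-event record. The record would show 0/23 for fever, with an exact two-sided 95% upper limit of 1 − 0.025^(1/23) = 14.8%. The full counts, with Clopper-Pearson limits, would be:
- 1/23 = 4.3% (0.1% to 21.9%)
- 2/23 = 8.7% (1.1% to 28.0%)
- 3/23 = 13.0% (2.8% to 33.6%)

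**The case against.** The strongest reply is that 4.6 adds a step and cancels nothing. It nowhere says that an unrelated fever is not an adverse event. Sections 15.1 and 15.6 are explicit, and a nurse can complete both the log and an adverse-event record. This stands to the extent that unrelated fevers can be missed but need not be. It does not remove the conflict: 4.6 sets the two records as alternatives, and it is the instruction staff will consult when a fever is reported.

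A reader might infer that fevers would vanish from the trial, or that a reported 0/23 would hide one to three cases. The documents do not support that. Temperature is collected from every subject at every scheduled time point, and the log reaches the sponsor, so fevers could be counted whatever the nurse decides.

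A reader might also infer that the 15.7 record is the only place where retention failures would be counted. That too goes beyond the text. Section 15.7 is a sponsor quality process and promises no count. Failures may also surface through daily comments, the Day 7 and Day 14 calls, and the confidence questions. It is true that the subject and nurse assessment forms do not ask whether a dressing actually leaked, moved or fell off, while the online survey in Appendix 2 does. That is a separate measurement question, which a new 15.3 definition would not answer.

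Two further limits stand. The pyrexia flow figure and procedure QP025, to which 15.6 refers for records, could not be examined and might add detail. The commitment to ISO 14155 and the duty in 15.7 also make it unlikely that staff would ignore an obvious garment failure.

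**Conclusion.** Both rules are wrong as written. Section 4.6 conflicts with 15.1 and 15.6, so an unrelated fever can be left out of the adverse-event record while remaining in the temperature data and the log. Section 15.3 repeats 15.2, so a harmless device failure without serious potential meets no stated definition.

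This is a safety-reporting fault, not an analysis choice. Adverse events are not among the endpoints in 6.1.3, so no planned endpoint estimate changes. The size of any under-count is unknown. The percentages in the working depend on assumed fever rates and counts, and on fevers staying only in the log, so they are not estimates for this study.

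Section 15.4 might be read as excluding a subject for any adverse event. Its heading and the handling in 4.3 point to serious events only, but the sentence is incomplete and only the sponsor can settle it. The point is worth correcting because the conflict is plain and the repair is short.

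**What to change.** 1. **Section 4.6:** replace the last two steps with: *Every pyrexia >38 degrees that meets 15.1, including every one that persists at the 1-hour recheck, is recorded as an adverse event and reported to the sponsor whatever its cause; relatedness is a field on that record; the telephone contact log is kept as a source document.* The device stop in 4.6 and the suspension in 6.3.4 stay as they are.
2. **Section 15.3:** replace the text with: *Any inadequacy or failure of the device, its labelling or instructions, including malfunction and use error, whether or not the subject was harmed.*
3. **Section 15.4:** the sponsor should complete the last sentence and state whether exclusion applies to serious adverse events only. Settle this together with change 1, so that recording a non-serious fever does not exclude a subject by accident.
4. **Section 15.5 (minor):** the heading names the unanticipated category (USADE) but the text defines a serious adverse device event (SADE). Align the two.

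The cost is a few short wording changes, a few more adverse-event and deficiency records, and possibly higher reported counts. No visits or measurements are added.

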5 OBJECTIVES AND HYPOTHESIS OF THE CLINICAL INVESTIGATION

5.1 Objectives

The objective is to evaluate the ease of use of Hidrawear AX compared to the subject's existing product use in 20 subjects with HS (Hidradenitis Suppurativa).

Secondary objectives are:

To establish the impact of wound care to patients using online survey.

To evaluate if Hidrawear AX:

- Is comfortable
- Improves quality of life
- Faster to use than the subject's existing product
- Reduces dressing related pain
- · Secure dressing retention

5.2 Hypothesis

When compared to standard methods of dressing the axilla, Hidrawear AX will be equivalent to or superior in terms of:

Ease of use

Comfort (wearing) to user

Time to apply

Dressing related pain and discomfort

Secure Dressing retention

And in turn will have a positive impact on the patient's quality of life.

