	Study Duration: 9 months - from when the study opens to enrolment until completion of data analyses			
	Subject participation duration: 3 weeks			
Sample size and study	Sample size: 23			
duration:	Female, over 18, presenting with HS of the axilla			
	Study Duration: 9 months - from when the study opens to enrolment until completion of data analyses			
	Subject participation duration: 3 weeks			

CR: 144

	In order to be eligible to participate in this study, an individual must meet all of the following criteria:				
	3				
	1. Provision of signed and dated informed consent form in English.				
	2. Stated willingness to comply with all study procedures and availability for the duration of the study				
	3. Female, aged >18				
	4. Diagnosed with Hidradenitis Suppurativa				
	5. Hidradenitis Suppurativa affecting the axilla				
	6. Exuding lesion that requires wound dressings				
	Exclusion Criteria:				
	1. Recent surgery <3 months in axilla				
1	2. Psoriasis, Dermatitis or skin conditions/rash other than Hidradenitis Suppurativa on or near affected area				
	3. Pregnancy or lactation				
	4. Known allergic reactions to components of Hidrawear AX				
Primary Performance					
Endneinter	Primary outcome measure:				
	Subjects own product use (Day 0) vs Hidramed (Day 21)				
	• Ease of Use Day 21 vs Day 0				
Secondary	Secondary outcome measures:				
Performance	 Ease of Use Day 21 vs Day 0 Comfort, measured 				
Endpoints:	on a 5-point scale Day 21 vs Day 0				
	 Visual Pain Analogue Scale Day 21 vs Day 0 				
	Time Day 21 vs Day 0				
	 Additional equipment used – mirror, scissors etc 				
	Could dressing be applied without raising arms over head				
	Necessity to stretch/contort body to apply dressing				
	Did subject need assistance				
	9 months - from when the study opens to enrolment until completion of data analyses.				
	Subject participation: 22 days, Visit day 0, and day 21.				

CE-GAX001-01

V4.0

CR: 144

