2.1 Description of the Investigational Device

HidraMed Solutions has developed an adhesive free wound dressing fixation device for people living with Hidradenitis Suppurativa (HS), a chronic and debilitating disease which causes non-healing lesions of the skin, mainly in the armpit, groin, thigh and buttocks - Hidrawear AX, designed to make dressing changes quick and easy for subjects.

The Hidrawear AX is designed to improve the wound care management for HS and chronic wound subjects. The unique features of the product completely remove the use of adhesives on the skin. Designed by a patient, for patients, Hidrawear AX provides comfort, ease of use and effective care for the every-day management of HS lesions.

The 3- part system is comprised of

- 1. The investigational device: the Hidrawear AX: A washable garment
- 2. An off-the-shelf dressing
- 3. An off-the-shelf mechanism to attach the dressing to the Hidrawear AX, such as a fastener supplied with the dressing or medical tape

The body conforming garment acts as a second skin and incorporates largely perforated panels over wound affected areas, minimising skin contact and aerating the area. The main function of the perforated is to act as a retaining device for the wound pads.

[figure not shown]

[figure not shown]
CE-GAX001-01

V4.0

CR: 144

The garment facilitates easy insertion, removal, precise positioning and adjustment of a non-adhesive wound dressing onto the effected wound space. The perforated section of the garment sits on the outer surface of the dressing providing provisional fixation. Next, an outer patch is placed on the outside of the garment on the footprint of the dressing. Through a hook and loop mechanism the dressing is now fully secured in place. It is designed so that quick, precise and pain free dressing changes can be achieved in less than 15 seconds

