3.4 Clinical Evaluation

This pilot study will evaluate usability - the safety, efficacy and performance of HidraWear AX in the home setting. Quality of life, ease of use and comfort of Hidrawear AX will be assessed.

The clinical effect of the wound pad will not be assessed. HldraWear AX does not claim wound healing but is a quicker and easier way to dress wounds.

CE-GAX001-01

V4.0

CR: 144

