5.3 Claims of Performance

Easy to use.

Comfortable.

Faster than existing products used.

Reduces pain.

Secure dressing retention

CE-GAX001-01

V4.0

CR: 144

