6.1.3 Primary and Secondary Endpoints

Primary Endpoint

• The change in the ease of use at week 3 compared to Day 0

Secondary Endpoints - Subject Assessment

- Ease of use W2 vs W1
- Comfort measured on a 10 point scale D21 vs D0
- Pain measured on a 10 point scale D21 vs D0
- Time measured on a 10 point scale D21 vs D0
- Dressing retention confidence measured on a 10 point scale D21 vs D0

Secondary Endpoints – Nurse Assessment

- Necessity to stretch/contort the body to apply dressing
- Did subject need assistance
- Could dressing be applied without raising arms over head
- Additional equipment used- mirror, scissors etc.

Outcome selection rationale:

- Assessment of ease of use as primary outcome was selected as most users have voiced frustration
- Comfort was selected as we wish to learn if Hidrawear AX is comfortable to use.
- Dressing retention confidence was selected as user have voiced frustration
- Dressing related pain was selected as HidraWear AX may reduce unnecessary patient distress due to dressing/adhesive related pain
- Time was selected as regular wound dressing changes are time consuming (6)

CE-GAX001-01

V4.0

CR: 144

DLQI was selected as it a validated tool that has been commonly used for assessment of quality of life for HS subjects. will assess if Hidrawear AX is better than the current products used by HS subjects.

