6.1.4 Methodology

Before the study commences on site, a survey will be shared into select closed patient groups online, to capture the patient experience of living with Hidradenitis Suppurativa (HS) in terms of self-managing wound care and the impact that HS wound care has on patients' day to day life, physically, financially and emotionally.

A secure and confidential survey tool (Typeform) will be used. This is governed under EU data legislation and encrypted to ensure privacy. The survey will not collect any identifying information and is a precursor to the HidraWear AX Pilot Study.

Day 0

Subjects will visit trial site or have a home visit from research nurse.

Following consent and enrolment, Subjects will be asked to demonstrate or explain their usual method of dressing their wound using their usual wound dressing products.

Subjects will assess this activity based on ease of use, comfort, experienced pain, confidence in dressing retention and time, using a 10 point visual analogue scale. (see appendix 2)

The subjects will complete a Dermatology Quality of Life Index Survey. (see appendix 5)

The research nurse will assess the activity based on whether the subject needs assistance, uses additional equipment, contorts or stretches their body, can dress the wound without raising their arms above their head. (See appendix 4)

Day 1-21

Daily Check in with Subjects:

Each day, at 1pm, subjects will receive an email requesting them to check in with the researcher by answering 3 questions.

- 1. What is your temperature?
- 2. How many dressings did you use in the last 24 hours?
- 3. Any comments?

This check in should take less than 5 minutes to complete.

Subjects will be required to respond by 5pm each evening. If subject has not responded by 5pm, a reminder text message will be sent to them.

If subject does not respond within 24 hours, the research nurse will call the subject to check in and take answers over the phone.

CE-GAX001-01

V4.0

CR: 144

Weekly Check in with Subjects:

On day 7 and 14 subjects will be asked to complete the Dermatology Quality of life survey and questions on Ease of use, comfort, pain and confidence, at home. A link to the surveys will be emailed to them at 1pm in the afternoon with their daily check in.

Subjects will be required to respond by 5pm each evening. If subject has not responded by 5pm, a reminder text message will be sent to them.

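### The plan sets out to show that HidraWear AX is faster, but it collects only a rating of perceived time; no dressing change is timed

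*Combined protocol and SAP*

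**What the plan says.** Several sections speak of speed:

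- Section 5.1 sets a secondary objective of evaluating whether the device is "Faster to use than the subject's existing product".
- Section 5.2 predicts that "Hidrawear AX will be equivalent to or superior in terms of" a list of outcomes that includes application time.
- Section 5.3, the claims of performance, has "Faster than existing products used".
- Section 3.4 says the device "is a quicker and easier way to dress wounds".
- Section 2.1 gives as a design aim that "quick, precise and pain free dressing changes can be achieved in less than 15 seconds".

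The measurement is described differently. The Clinical Investigation Summary lists "Time Day 21 vs Day 0" with no unit or instrument. Section 6.1.3 has "Time measured on a 10 point scale D21 vs D0", and section 6.1.4 makes this a subject-completed 10-point visual analogue scale at Day 0 and Day 21. On the forms in Appendices 3 and 4 the subject rates how time consuming a change is. For the Day 0 activity, section 6.1.4 states: "Subjects will be asked to demonstrate or explain their usual method of dressing their wound".

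**The concern.** Faster is a statement about duration. The planned outcome is an opinion about duration, given by subjects who know which product they are rating and are comparing their old one with a new one. If the rating improves, the natural report under section 5.3 is that the device is faster, although nobody will have measured how long a change takes with either product. The bare wording of the time endpoint in the summary makes that misreading easier.

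There is a second difficulty. A subject who only describes her usual method at Day 0 rates it from memory. At Day 21 she rates a change she has just carried out. The difference between the two ratings would then mix product with mode of assessment.

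**Working it through.** The plan gives no figure for time, so there is none to reproduce. The check is to go through every planned instrument and ask whether it holds a duration that can be paired within subject.

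| Instrument | Time content | Paired duration? |
|---|---|---|
| Subject form, Day 0 (Appendix 3) | Rating of how time consuming, usual product | No |
| Subject form, Day 21 (Appendix 4) | Same rating, HidraWear AX | No |
| Nurse forms, Day 0 and Day 21 (Appendix 5) | None: contortion, assistance, arm raising and extra equipment (Day 0 also records the dressings used) | No |
| Daily check-in (Appendix 7) | None: temperature, number of dressings, comments | No |
| Schedules (6.4.1, Appendix 1) | Time listed with the other subject-rated items | No |
| Online survey (Appendix 2, section 3, question 11) | Banded minutes | No, see below |

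**The survey.** Section 3.1 mentions comparison with survey data, so the one item in minutes needs a closer look. It fails on four counts:

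- It asks for a daily total, not time per change.
- It includes tending to lesions as well as dressing them.
- It concerns current care, so it contains nothing on HidraWear AX.
- Section 6.1.4 says no identifying information is collected, so answers cannot be linked to trial subjects.

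**The activity rated.** Section 5.2 refers to application. The instructions in Appendices 3 and 4 refer to a full change, which would also cover removal of the old dressing. These are different intervals, and no section chooses between them.

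**Whether it is performed.** Sections 6.1.4 and 4.4 let the subject show or merely describe her method at Day 0. Appendix 3 instructs her to dress the wound, and section 6.4.1 and Appendix 1 both list observation of the usual method. At Day 21, section 6.1.4 asks for a demonstration only. The Day 0 passages conflict with one another, and one reading of them does not match Day 21.

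**What timing would yield.** The half-width of a 95% CI for a paired mean change, in SDs of the paired difference, is t(0.975, n−1)/√n.

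- n = 23: 2.074/4.796 = 0.43 SD.
- n = 17 (23 − 6 anticipated drop-outs, none replaced, although section 6.3.6 plans replacement): 2.120/4.123 = 0.51 SD.

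These widths depend only on n and are the same for a rating as for seconds. They show the precision available if changes were timed, and do not measure the present gap. The documents give no SD, so the widths cannot be turned into seconds.

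**The case against.** The best defence is that perceived time is what the study means to measure. Sections 6.1.3 and 6.1.4 and the subject forms agree on it, section 3.4 describes a usability study, and the stated reason for choosing the outcome is the burden of frequent changes. Section 5.1 asks whether the device is faster and does not assert it. All of this stands: perceived time is a legitimate usability outcome and should be kept. It does not rescue the wording in section 5.3, which is a claim about speed, or the reference to application time in section 5.2.

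The scale graphics are not visible in the text available, so the anchors cannot be checked. Even if they mentioned minutes, the answer would still be a subject's own estimate on a 10-point scale.

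A reader might go further and infer that the hypothesis in section 5.2 is defective because it has no equivalence margin. The documents do not support that as a serious fault. Section 7.1 describes a small preliminary study meant to supply estimates, section 7.2 sets the size by feasibility, section 7.3 disclaims a power calculation, and no test is planned. The 0.18 in section 7.2 is a precision figure for the primary response and was never offered as a margin.

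A reader might also infer that the study fails to verify the 15-second figure. Section 2.1 states a design aim. It is not an objective, an endpoint or a section 5.3 claim, and section 4.6 refers to verification and validation testing of the garment design. This study does not test the figure and needs no separate analysis of it.

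**Conclusion.** The point holds in a limited form. As planned, the trial can say whether subjects perceive dressing changes as less time consuming with HidraWear AX. It cannot say whether they are faster, because no planned trial record contains a duration: there would be no timed pairs from 23 subjects. The possible mismatch between a described change at Day 0 and a performed one at Day 21 weakens even the perceived-time comparison, to a degree the documents do not allow one to estimate.

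The conclusion rests on reading the time item as a subjective rating, which section 6.1.3 and the item wording support. It does not invalidate the pilot, affects neither the primary outcome nor the sample size, and is best settled before the first Day 0 visit. A minor consequence of the wording in section 5.2 is that a non-significant change should not be reported as equivalence.

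**What to change.** Choose one of two routes.

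**(a) Measure it.** Add start and stop times to both Appendix 5 nurse forms, and a Day 0 box for *performed* or *explained only*. Write one definition of the timed interval for both products: application only, or a full change. Report the paired Day 21 minus Day 0 difference in seconds with a 95% CI, in subjects who performed the change at both visits, and state how many did not. Keep the 10-point rating as perceived time. The comparison remains an unblinded before-after one and should be described as such.

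**(b) Reword it.** Replace the speed wording in sections 5.1 and 5.3, and application time in section 5.2, with perceived time, for example *perceived as less time consuming*.

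Under either route, reconcile sections 4.4 and 6.1.4 with Appendix 3, section 6.4.1 and Appendix 1 on what happens at Day 0. Report all outcomes as descriptive paired estimates with CIs.

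Route (b) costs only wording. Route (a) adds a few fields to forms the nurse already completes at two planned visits, with no extra visit. Its drawbacks are slightly more form work, possibly fewer than 23 timed pairs (those who only explain at Day 0 drop out of the comparison and may not be typical), and a speed claim that may turn out not to be supported.
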